## 1 PROTOCOL SUMMARY

### 1.1 SYNOPSIS

Title:	WeExPAnd: PrEP Demonstration Project Among Women at Risk for HIV Infection - Preexposure Prophylaxis (PrEP)
Study Description:	This is a prospective, mixed-methods pilot demonstration study using a pre-/post-intervention design to assess the feasibility, acceptability, and preliminary impact of a culturally adapted patient-provider communication tool on PrEP uptake among cisgender women receiving care at federally qualified health centers (FQHCs) in Alabama. The study employs an iterative implementation process guided by the Exploration, Preparation, Implementation, and Sustainment (EPIS) framework and Dynamic Adaptation Process (DAP).
Objectives:	Primary: To assess the feasibility, acceptability, and preliminary impact of an adapted patient-provider communication intervention on PrEP uptake among cisgender women Secondary: To evaluate PrEP medication adherence and clinic visit adherence
Endpoints:	Primary: PrEP uptake rates, intervention feasibility metrics (recruitment numbers, enrollment rate (proportion of eligible participants consenting), participant retention (proportion completing 3-month follow-up), PrEP referral acceptance rate, and intervention delivery completion rate), and intervention acceptability measures (patient satisfaction surveys) Secondary: PrEP adherence (self-report via Visual Analogue Scale), clinic visit adherence (attendance rates)
Study Population:	Cisgender, HIV-uninfected women aged 18 years or older who are English-speaking and report sexual activity or anticipate sexual activity within 6 months.
Phase:	N/A

Description of Study Intervention:	Participants receive a brief patient-provider communication intervention using an adapted flip-book communication tool, optionally preceded by a 3-minute PrEP informational video. The intervention facilitates structured conversations about HIV risk assessment and PrEP as a prevention option, with referrals to PrEP services for interested participants.
Study Duration:	Approximately 18 months for enrollment and intervention implementation, with a 12-month follow-up for outcome assessment
Subject Duration:	Up to 3 months active participation (baseline assessment, intervention visit, 3-month follow-up), with medical record data abstraction at 3 months and 12 months post-intervention

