## 1.2 SCHEDULE OF ACTIVITIES (SOA)

Study Activity	Screening	Baseline (Day 0)	Intervention Visit	3-Month Follow-up	12-Month Data Collection
Eligibility Assessment	x				
Informed Consent		x			
Demographics		x			
Baseline Assessments*		x			
PrEP Video (optional)			x		
Patient-Provider Communication Tool			x		
PrEP Referral (if interested)			x		
Patient Satisfaction Survey			x		
3-Month Assessments**				x	
Qualitative Interview				x	

Medical Record Abstraction***				x	x
Adverse Event Assessment		x	x	x	

Notes:

\*Baseline Assessments include: intimate partner violence, depression, anxiety, substance use, sexual behaviors, HIV knowledge, PrEP awareness, social support, spirituality/religiousness, PTSD screening

\*\*3-Month Assessments include: depression, anxiety, substance use, sexual behaviors, HIV knowledge, intimate partner violence, PrEP adherence (if applicable), stage of change

\*\*\*Medical record data abstraction includes PrEP initiation and clinic visit attendance

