### 4.3 STRATEGIES FOR RECRUITMENT AND RETENTION

**Recruitment Methods:** Patient recruitment occurs through three approaches: (1) research assistant pre-screening of electronic medical records to identify potentially eligible patients with upcoming clinic visits; (2) recruitment flyers posted in clinic waiting areas; and (3) direct referral by healthcare providers at participating clinics.

Patients recruited through EMR pre-screening are formally screened during routine clinic visits. Patients recruited via flyers or provider referral either contact the research assistant directly using the phone number on flyers or provide permission to be contacted by study staff for telephone screening.

**Retention Strategies:** Participants receive compensation at each study visit (\$30 baseline, \$30 intervention, \$40 three-month follow-up). Reminder calls are conducted 24 hours before scheduled visits. Flexible scheduling options are provided for follow-up assessments, including in-person or telephone completion.

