## 5 STUDY INTERVENTION

### 5.1 STUDY INTERVENTION(S) ADMINISTRATION

#### 5.1.1 STUDY INTERVENTION DESCRIPTION

The study intervention consists of a brief patient-provider communication session using a culturally adapted flip-book communication tool, optionally preceded by a 3-minute PrEP informational video. The intervention facilitates structured conversations about HIV risk assessment and PrEP as a prevention option.

During the intervention visit, participants may first watch the informational video about PrEP. The trained study provider then follows up on video content and uses the flip-book communication tool to guide discussion about HIV risk, PrEP candidacy, and prevention options. The session concludes with referral to PrEP services for interested participants or discussion of alternative risk-reduction strategies for those not interested in PrEP.

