# 7 STUDY ASSESSMENTS AND PROCEDURES

## 7.1 STUDY ASSESSMENTS

**Baseline Assessments (completed prior to intervention):** Demographics, intimate partner violence (Abuse Assessment Screen), depression (CES-D-10), anxiety (State-Trait Anxiety Inventory), substance use (Addiction Severity Index-Lite), sexual behaviors, HIV transmission knowledge, PrEP awareness, social support (MOS Social Support Survey), spirituality/religiousness (Ironson-Woods Scale), and trauma screening.

**Post-Intervention Assessments:** Patient satisfaction with intervention (Client Satisfaction Questionnaire CSQ-8) completed immediately following the intervention session.

**3-Month Follow-up Assessments:** Repeat measures of depression, anxiety, substance use, sexual behaviors, HIV knowledge, intimate partner violence, PrEP adherence (if applicable), and stage of change. Qualitative interview exploring study experience and PrEP decision-making.

**Medical Record Data Collection:** PrEP initiation and clinic visit attendance abstracted at 3 months and 12 months post-intervention.

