## 8.3 STATISTICAL ANALYSES

### 8.3.1 GENERAL APPROACH

Quantitative data will be analyzed using SPSS or R. Descriptive statistics will summarize all collected data. As this is a pilot feasibility study, analyses will focus on estimation rather than hypothesis testing, with emphasis on confidence intervals for key parameters.

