### 8.3.2 ANALYSIS OF THE PRIMARY EFFICACY ENDPOINT(S)

**Intervention feasibility:** Feasibility will be assessed using descriptive statistics (i.e., counts and proportions) for: recruitment numbers (number of participants screened), enrollment rate (proportion of eligible participants consenting), participant retention (proportion completing 3-month follow-up), PrEP referral acceptance rate (proportion accepting referral among those offered), and intervention delivery completion rate (proportion receiving complete intervention). Reasons for non-participation, referral decline, and incomplete intervention delivery will be summarized using frequency distributions and percentages.

**Intervention acceptability.** Acceptability will be assessed using descriptive statistics (mean and standard deviation) for CSQ-8 scores among patient participants. Missing item responses will be handled according to each instrument's scoring guidelines.

**PrEP uptake changes.** PrEP uptake rates will be compared between the 7-month pre-intervention period and the post-period using binomial logistic regression. Time period (pre-intervention vs. post) will serve as the primary predictor. Uptake proportions (i.e., patients who initiate PrEP over eligible patients referred) and 95% confidence intervals will be calculated to estimate the change in uptake rates between periods.

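### The pre/post PrEP uptake contrast is taken over referred women, so it may measure initiation after referral and miss a gain that comes through more referrals

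*Combined protocol and SAP*

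**What the plan says.** Section 8.3.2 compares uptake between a 7-month pre-intervention period and the post-period by logistic regression on time period. The quantity compared is given in the same paragraph: "Uptake proportions (i.e., patients who initiate PrEP over eligible patients referred) and 95% confidence intervals will be calculated". The regression denominator is not stated separately, but these proportions are the ones used to estimate the change between periods.

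Three places describe referral as part of the intervention and conditional on interest:

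- Section 1.1: "with referrals to PrEP services for interested participants".
- Section 1.2, in the intervention visit column: "PrEP Referral (if interested".
- Section 5.1.1: "The session concludes with referral to PrEP services for interested participants". Women who are not interested discuss other ways to reduce risk instead.

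Section 8.3.2 also lists a feasibility measure that separates offer from acceptance, "PrEP referral acceptance rate (proportion accepting referral among those offered", and plans to summarise why referrals are declined.

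The hypothesis in section 8.1 concerns uptake among participants. The precision example in section 8.2 takes 25% of 125 participants. Initiation is collected from records: "PrEP initiation and clinic visit attendance abstracted at 3 months and 12 months post-intervention". No other pre/post uptake contrast is named.

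**The concern.** Uptake among eligible women is the product of two steps: the share referred, and initiation among those referred. The session is built to start a conversation that ends in referral, so the first step is the one it acts on most directly. A contrast conditional on referral keeps only the second step. If the session brings more women to referral and they start PrEP at the same rate as before, the planned odds ratio is 1. If the additional women start less often, it falls below 1 although more women start PrEP.

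Uptake is one of the co-listed primary endpoints, and this is the only planned pre/post estimate of preliminary impact. The pilot is meant to inform a larger trial, so a conversion rate read as uptake could mislead that design. The post-period percentage taken alone could also look well above the share of participants who start.

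**Working it through.** **Inputs from the documents.** N = 125, 25% initiating and an interval width of about 15.8% (section 8.2); the uptake definition (section 8.3.2). Every referral rate, initiation rate and coverage rate below is an assumption.

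**1. The plan's own figure.** The exact (Clopper-Pearson) 95% limits for x out of n are the 0.025 quantile of Beta(x, n − x + 1) and the 0.975 quantile of Beta(x + 1, n − x). For 31/125 = 24.8% they are 17.5% and 33.3%, a width of 15.8 points. Section 8.2 reproduces, with all participants as the denominator.

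**2. Same 31 initiators, different denominators.**

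| Denominator | n | Proportion | Exact 95% CI |
|---|---|---|---|
| All enrolled, or all referred | 125 | 24.8% | 17.5 to 33.3 |
| About 90% referred | 112 | 27.7% | 19.6 to 36.9 |
| 60% referred | 75 | 41.3% | 30.1 to 53.3 |
| 40% referred | 50 | 62.0% | 47.2 to 75.3 |

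**3. The pre/post contrast.** Let r be the share of eligible women referred and i the initiation proportion among them, with subscript 0 for pre and 1 for post. Uptake over eligible women is p = r × i.

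- Planned OR = [i₁/(1 − i₁)] / [i₀/(1 − i₀)]
- OR over eligible women = [p₁/(1 − p₁)] / [p₀/(1 − p₀)], taking all eligible post-period women to have had the session

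| Assumed r | Assumed i | p | Planned OR | OR over eligible |
|---|---|---|---|---|
| 20% → 50% | 50% → 50% | 10% → 25% | 1.00 | (0.25/0.75)/(0.10/0.90) = 3.00 |
| 20% → 50% | 50% → 40% | 10% → 20% | (0.40/0.60)/(0.50/0.50) = 0.67 | (0.20/0.80)/(0.10/0.90) = 2.25 |
| 20% → 20% | 40% → 50% | 8% → 10% | (0.50/0.50)/(0.40/0.60) = 1.50 | (0.10/0.90)/(0.08/0.92) = 1.28 |

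In the second row uptake doubles while the planned OR points the other way. In the third row the referred share is equal, and the ratio of proportions is 1.25 on either denominator; only the odds ratios differ.

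A wider assumed change shows the range. With 125 eligible women per period, referrals rising from 10 to 60 and initiators from 5 to 30, the planned OR is 1.00 and the OR over eligible women is 7.58 (4.0% to 24.0%).

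**4. Dilution of a clinic-wide contrast.** If only a share s of eligible women have the session, the first row becomes p₁ = 0.25s + 0.10(1 − s). For s = 50%, 25% and 10%, p₁ is 17.5%, 13.75% and 11.5%, and the OR over eligible women falls from 3.00 to 1.91, 1.43 and 1.17.

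**The case against.** The strongest reply is that *referred* may mean offered a referral. Section 8.3.2 separates offer from acceptance and tracks declined referrals, so some women are offered a referral they do not want. If nearly every participant is offered one, the post-period proportion is close to the all-participant one (27.7% against 24.8% at about 90%). This stands, and it makes the point conditional. It does not settle it: sections 1.1, 1.2 and 5.1.1 tie referral to interest, the offer rate is not given, and a different offer rate in the pre-period would still matter.

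*Eligible* is open too. The session covers PrEP candidacy (section 5.1.1), while section 4.1 requires no PrEP indication and section 4.2 does not name current PrEP use as an exclusion. If *eligible* means PrEP candidates, an all-enrolled denominator may include women who cannot newly start. That estimate should therefore sit beside the planned contrast and not replace it. It also has no pre-period comparator, so it limits misreading without supplying a before/after comparison.

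The plan's general statement, "Descriptive statistics will summarize all collected data", allows initiators over all enrolled to be reported, but section 8.3.2 does not name that as an uptake estimate. The single-arm pilot design, focused on estimation, limits the harm.

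A reader might infer that the width in section 8.2 is wrong. It is not: it reproduces, is offered as an example, and makes no claim about the pre/post contrast.

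**Conclusion.** The point holds conditionally. Unless nearly all eligible women are referred (or offered referral) in both periods, or the referred share is the same in both, the planned contrast describes initiation after referral and should not be read alone as change in uptake. It can then show no effect, or the opposite effect, when more women start PrEP: 1.00 against 3.00, or 0.67 against 2.25, under the assumed rates.

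A reader might go further and conclude that the planned estimate is certainly biased, or that it can never reflect uptake. The documents do not support that. They give no referral rate and no pre-period rate, so neither size nor direction can be derived, and the undefined terms leave room for a reading under which the two measures nearly coincide. Nor does anything suggest that the two periods would use different definitions; the definitions are simply not stated. This should be corrected before analysis, and the correction is mostly wording.

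**What to change.** In section 8.3.2:

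- **(a)** Beside the planned contrast, report post-period initiators over all enrolled women with an exact 95% interval. State which abstraction time point is used (3 or 12 months) and how women already on PrEP are counted. Say that this estimate has no pre-period comparator.
- **(b)** Label initiated over referred as conversion after referral, and do not interpret it alone as change in uptake. Give one definition of *eligible*, and one of *referred* (offered or accepted), for both periods.
- **(c)** Report the numbers referred and the numbers initiating separately for each period.
- **(d)** Only if records give a count of potentially eligible clinic women for both periods, add initiators over that count as a supporting pre/post contrast. State that it is a proxy, since the self-reported criteria in section 4.1 cannot be applied to records, and that women who did not receive the session dilute it.

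**Cost.** Items (a) to (c) are changes of wording. They use the planned abstraction and the referral counts that the contrast already needs. The headline percentage will be lower whenever not all women are referred (24.8% instead of 41.3% in the example with 75 referred). Item (d) needs one further record count per period, which may not be obtainable, and its estimate is pulled towards 1.

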### 8.3.3 ANALYSIS OF THE SECONDARY ENDPOINT(S)

**PrEP adherence.** PrEP adherence will be measured with Visual Analog Scale scores from the ACTG Adherence Questionnaire among participants who initiate PrEP. Adherence will be evaluated through descriptive statistics (i.e., counts) of patients' self-perceived PrEP prescription regimen adherence and descriptive statistics (i.e., means and standard deviation) of patients' estimated PrEP dosage adherence. Adherence scores are collected at the 3-month timepoint.

**Clinic visit adherence.** Clinic visit adherence will be assessed using descriptive statistics (i.e., mean and standard deviation) for the ratio of PrEP visits attended to PrEP visits scheduled among patients who initiate PrEP. Adherence ratios were collected at 3-month and 12-month follow-up timepoints.

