#### Secondary Hypotheses:

- Participants who initiate PrEP will demonstrate adequate medication adherence and clinic visit adherence

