## 8.2 SAMPLE SIZE DETERMINATION

The target sample size of N=125 patient participants provides reasonable precision for estimating feasibility and acceptability measures in this pilot study. For instance, assuming 25% of participants initiate PrEP, the 95% confidence interval width for this proportion would be approximately 15.8%. This sample size is adequate for a pilot study aimed at informing the design of a future larger-scale trial rather than testing definitive efficacy hypotheses.

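### Does counting the visit at which PrEP is started inflate clinic visit adherence among initiators?

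*Combined protocol and SAP*

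**What the plan says.** Section 8.3.3 defines clinic visit adherence as "the ratio of PrEP visits attended to PrEP visits scheduled among patients who initiate PrEP" and summarises it by a mean and standard deviation. Each initiator therefore has equal weight, however many visits she had booked. On timing it says "Adherence ratios were collected at 3-month and 12-month follow-up timepoints".

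The data come from the medical record. Section 7.1 has "PrEP initiation and clinic visit attendance abstracted at 3 months and 12 months post-intervention", and the synopsis (1.1) agrees: "with medical record data abstraction at 3 months and 12 months post-intervention". The clock thus starts at the intervention and not at PrEP initiation. Initiation may come some time later, because under 5.1.1 "The session concludes with referral to PrEP services for interested participants".

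The hypothesis served is in 8.1: "Participants who initiate PrEP will demonstrate adequate medication adherence and clinic visit adherence". No figure is given for what counts as adequate. The documents do not define a PrEP visit or PrEP initiation, and they give no rule for a woman with no countable scheduled visit.

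**The concern.** The analysis set is chosen on having initiated PrEP. If initiation happens at a scheduled PrEP visit, that visit was attended by construction and says nothing about later attendance. Counting it would mean that no such initiator can score 0 and that a woman with no later booking scores 100%. Because per-woman ratios are averaged, her 1/1 weighs as much as the record of a woman with many bookings.

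The 3-month figure looks most exposed. A woman who is referred, waits, and starts shortly before the 3-month abstraction may have had no time for another visit. The result at stake is the visit adherence estimate reported for initiators, which could look better than their attendance after starting.

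**Working it through.** **The plan's own figure.** Section 8.2 takes N = 125 and works by "assuming 25% of participants initiate PrEP", with a 95% interval about 15.8% wide. An exact (Clopper-Pearson) interval for 31/125 has width 15.80%, so the figure reproduces; the simple normal formula gives 2 × 1.96 × √(0.25 × 0.75/125) = 15.2%. This does not bear on the ratio, but it gives the expected number of initiators: 0.25 × 125 = 31.25, about 31.

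**Inputs the documents do not give.** Let k be the number of later visits booked and p the probability that each is attended. All values below are assumed.

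**Step 1: initiating visit counted, no earlier missed booking.** The expected ratio is (1 + kp)/(1 + k), against p if that visit is left out. The difference is (1 − p)/(k + 1).

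| p | k = 1 | k = 2 | k = 4 |
|---|---|---|---|
| 50% | 75% (+25 points) | 67% (+17) | 60% (+10) |
| 90% | 95% (+5) | 93% (+3) | 92% (+2) |

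With p = 0 the ratio is 1/(k + 1): 50% for k = 1 and 20% for k = 4.

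**Step 2: no later booking (k = 0).** Counted, the ratio is 1/1 = 100%. Left out, it is 0/0 and the woman drops from the mean. Let a share s of initiators be in this position and the rest have p = 50%. The mean with the visit counted is s + (1 − s)(1 + 0.5k)/(1 + k).

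| s | k = 1 | k = 4 | Women contributing if the visit is left out |
|---|---|---|---|
| 20% | 80% | 68% | 0.8 × 31.25 = 25 |
| 40% | 85% | 76% | 0.6 × 31.25 ≈ 19 |
| 60% | 90% | 84% | 0.4 × 31.25 = 12.5 |

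With the visit left out, the mean is 50% in every row.

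**Step 3: the same window, with one booking missed before initiation.** A count that starts at the intervention takes in every PrEP appointment from then on, including one made after referral and missed. The ratio becomes (1 + kp)/(k + 2), which differs from p by (1 − 2p)/(k + 2).

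| p | k = 1 | k = 4 |
|---|---|---|
| 50% | 50% (0 points) | 50% (0) |
| 90% | 1.9/3 = 63% (−27) | 4.6/6 = 77% (−13) |

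A woman with one earlier miss and no later booking scores 1/2, not 1/1. With one earlier miss, the difference is positive only when p is below 50%.

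**Step 4: the other readings.** Section 7.1 lists initiation and attendance as separate items, and 8.1 speaks of adherence in women who have initiated. Neither settles the matter, but both fit a count of visits after initiation, under which the effect is zero. If PrEP is started without a separate scheduled PrEP visit, the effect is also zero. If the initiating visit was unscheduled and entered the numerator only, ratios above 1 could appear and would show that the count needs attention.

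**Step 5: timing.** The lack of time for a further visit mainly affects the 3-month ratio. A woman who starts just before the 3-month abstraction has 12 − 3 = 9 more months of possible bookings before the second.

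**The case for a change.** The strongest case for changing the text is that it gives an abstractor no instruction to leave the initiating visit out. The window contains that visit, and the whole analysis set is selected on initiation. Section 8.3.1 makes estimation the purpose, "with emphasis on confidence intervals for key parameters", so an estimate whose meaning hangs on an unstated rule sits badly with the plan's own aim. With about 31 initiators, a few scores of 1/1 can move the mean. Leaving the visit out without a further rule only turns 100% into 0/0. A sentence or two would settle it at almost no cost.

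Much of this stands. The rule is not written down, the arithmetic in Steps 1 and 2 is right, and where the visit is scheduled, attended and counted, a score of 0 is impossible. What does not stand is the step from there to an inflated result. It requires initiation to occur at a scheduled PrEP visit, that visit to be counted, and few or no missed bookings before it. The documents support none of these in particular. Nor is a restriction to later visits free of cost: it removes missed appointments between referral and initiation, which a reader interested in linkage to PrEP care might want kept, and it leaves fewer women contributing, above all at 3 months. Reporting how many initiators had no later booking, or a separate measure of attendance near 12 months, would be useful extra description, but neither corrects a rule shown to be wrong.

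**Conclusion.** No change to the plan follows. Section 8.3.3 leaves a counting convention unstated; it does not prescribe a biased one. Depending on assumed inputs, the ratio could sit 25 points above attendance after initiation (p = 50%, one later visit, no earlier miss), 27 points below it (p = 90%, one later visit, one earlier miss), or exactly on it if only later visits are counted. None of these inputs is in the documents, so neither the size nor the sign of an effect can be claimed.

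The consequence is small in any case. The endpoint is secondary and descriptive, adequacy has no numerical threshold, no decision depends on the ratio, and the primary feasibility, acceptability and uptake results are untouched. An analyst who meets a one-visit or zero-visit denominator will have to choose a convention, can do so from the records being abstracted, and would ordinarily state it with the number of women contributing. This conclusion rests on the ratio remaining a descriptive summary. It would need another look if the ratio were later used as a go/no-go criterion or read as persistence in PrEP care.
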